7.4.1.2 Methods of Recording and Assessing Adverse Events

At each trial visit, the subject will be queried on changes in his/her condition. During the reporting period of the trial any unfavorable changes in the subject’s condition will be recorded as AEs, whether reported by the subject or observed by the investigator.

Complete, accurate and consistent data on all AEs experienced for the duration of the reporting period (defined below) will be reported on an ongoing basis in the appropriate section of the CRF. Among these AEs, all serious AEs or unexpected non-serious ADRs must be additionally documented and reported using an Adverse Event Safety Report Form as described in Section 7.4.1.4.

It is important that each AE report include a description of the event, its duration (onset and resolution dates [and times, when it is important to assess the time of AE onset relative to the recorded treatment administration time]), its severity, its relationship with the trial treatment, any other potential causal factors, any treatment given or other action taken (including dose modification or discontinuation of the IMP[s]) and its outcome. In addition, serious cases should be identified and the appropriate seriousness criteria documented.

Specific guidance can be found in the CRF Completion and Monitoring Conventions provided by the Sponsor.

7.4.1.3 Definition of the Adverse Event Reporting Period

The adverse event reporting period for safety surveillance begins when the subject is included into the trial (date of first signature of informed consent) and continues through the trial's post treatment follow-up period, defined as the complete of the last visit.

7.4.1.4 Procedure for Reporting Serious Adverse Events and Non-serious Adverse Drug Reactions

In the event of any new SAE or new non-serious ADR occurring during the reporting period, the Investigator must immediately report to Merck Serono Global Drug Safety Department by telephone, by fax or by emails within a maximum 24 HOURS after becoming aware of the event.

Names, addresses, telephone and fax numbers for AE reporting as follows:

Merck Serono Global Drug Safety Department

Address: Merck KGaA, [name];

Email: [contact]

[contact];

[contact];

When an SAE or its follow-up information is reported by telephone, a written report must be sent immediately thereafter by fax or e-mail.

Reporting procedures and timelines are the same for any new information on a previously reported SAE (= follow-up).

All written reports should be transmitted with the Adverse Event Safety Report Form (Clinical Trials), which must be completed by the Investigator following specific completion instructions.

The AE section of the CRF must be completed, and a copy of the information must be transmitted along with the Adverse Event Safety Report Form (Clinical Trials). Other relevant pages from the CRF may also be provided (e.g., medical history, concomitant drugs).

The Investigator/reporter must respond to any request for follow-up information (e.g., additional information, outcome, final evaluation, other records where needed) or to any question the Sponsor may have on the AE within the same timelines as initial reports. This is necessary to ensure that the Sponsor promptly assesses the event and, where applicable, meets the regulatory timelines for expedited safety reporting.

Requests for follow-up will usually be made by the responsible Monitor. In exceptional cases where a particularly critical event occurs, the Global Drug Safety department may contact the Investigator directly for further information or discussion.

7.4.1.5 Safety Reporting to Health Authorities, Independent Ethics Committees and Investigators

The Sponsor will send appropriate safety notifications to Health Authorities in accordance with applicable laws and regulations.

The Investigator must report SAEs (particularly deaths) in accordance with applicable site-specific requirements to the IEC that approved the trial.

In accordance with the ICH GCP guidelines, the Sponsor will immediately inform all the trial Investigators and the Heads of the trial sites of “findings that could adversely affect the safety of subjects, impact the conduct of the trial or alter the IEC’s approval/favorable opinion to continue the trial.” In particular and in line with respective applicable regulations, the Sponsor will immediately inform all the trial Investigators and the Heads of the trial sites of AEs that are both serious and unexpected and are considered to be related to the administered product (“suspected unexpected serious adverse reactions” or SUSARs). In addition, according to applicable regulations, the Sponsor will inform the trial Investigators and the Heads of the trial sites of all SAEs which were reported to the health authorities. The investigator should place copies of the safety reports in the Investigator Site File. The Head of the trial site should also maintain copies of safety reports appropriately.

When specifically required by regulations and guidelines, the Sponsor will provide appropriate safety reports directly to the concerned lead IEC and will maintain records of these notifications. When direct reporting by the Sponsor is not clearly defined by national or site-specific regulations, the Investigator will be responsible for promptly notifying the concerned IEC of any safety reports provided by the Sponsor and for filing copies of all related correspondence in the Investigator Site File.

7.4.1.6 Monitoring of Subjects with Adverse Events

Any AE that occurs during the course of a clinical trial and is considered to be possibly related to the IMP must be monitored and followed up by the Investigator until stabilization or until the outcome is known, unless the subject is documented as “lost to follow-up”. Reasonable attempts to obtain this information must be made and documented. It is also the responsibility of the Investigator to ensure that any necessary additional therapeutic measures and follow-up procedures are performed. The Sponsor will actively follow-up and collect information on any AE that occurs during the course of a clinical trial, however while this activity will continue for any serious AEs until stabilization or until the outcome is known, it will be discontinued at the time of database lock for non-serious AEs.

7.4.2 Pregnancy and In Utero Drug Exposure

Pregnancies are not considered per se to be adverse events. However, all pregnancies with an estimated conception date during the period defined in Section 7.4.1.3 must be recorded by convention in the AE page/section of the CRF. The same rule applies to pregnancies in female subjects and in female partners of male subjects. The Investigator must notify the Sponsor in an expedited manner of any pregnancy using the Pregnancy Report Form, which must be transmitted according to the same process as described for SAE reporting in Section 7.4.1.4.

Investigators must actively follow up, document and report on the outcome of all these pregnancies, even if the subjects are withdrawn from the trial.

The Investigator must notify the Sponsor of these outcomes using the Pregnancy Report Form, and in case of abnormal outcome, the Adverse Event Safety Report Form (Clinical Trials) when the subject sustains an event and the Parent-Child/Fetus Adverse Event Report Form when the child/fetus sustains an event).

Any abnormal outcome must be reported in an expedited manner as described in Section 7.4.1.4, while normal outcomes must be reported within 45 days from delivery.

In the event of a pregnancy in a subject occurring during the course of the trial, the subject must be discontinued from trial medication immediately. The Sponsor must be notified without delay and the subject must be followed as mentioned above.

7.4.3 Laboratory Assessments

All laboratory assessments have been detailed listed in Section 7.1 and Section 7.2.

7.4.4 Vital Signs, Physical Examinations, and Other Assessments

All vital signs, physical examinations, and other assessments have been detailed listed in Section 7.1 and Section 7.2.

7.5 Pharmacokinetics

Not Applicable.

7.6 Biomarkers/Pharmacogenetics (PGX)

Not Applicable.

7.7 Other Assessments

Not Applicable.

8 Statistics

8.1 Sample Size

This is an open-label, single arm trial intended to evaluate the improvement of microvascular function (myocardial blood flow reserve, MFR) by positron emission tomography (PET) after twelve week treatment with oral nicorandil in female non-obstructive CAD patients. The null hypothesis is that there is no difference between MFR at baseline and MFR after twelve weeks treatment. The alternative hypothesis is that the MFR after twelve weeks treatment is higher than the MFR at baseline.

Suppose the difference of MFR follows normal distribution, and the following assumptions are made to determine the sample size:

The mean value of difference of MFR is 0.55.

The standard deviation of difference of MFR is 0.56.

Alpha=0.05(two sided).

Power=0.80.

A sample size of 11 patients will be required to reach this goal. Assuming a drop-out rate of 30%, then a total of 15 patients will be recruited into this study. According to the recruitment progress, if there have been 11 patients complete their following period, this study could be accomplished when meet the end of the anticipated period of the whole study.

8.2 Randomization

Not available.

8.3 Endpoints

8.3.1 Primary Endpoint

The primary endpoint is the difference of MFR by stress PET between baseline and after twelve-week treatment.

8.3.2 Secondary Endpoints

The secondary endpoints in this study include

The difference of myocardial blood flow (MBF) by rest PET between baseline and twelve weeks treatment.

The difference of myocardial blood flow (MBF) by stress PET between baseline and twelve weeks treatment.

The parameters of heart function by echocardiography: Cardiac systolic function: Ejection Fraction (EF%), left ventricular end systolic dimension (LVESD), left ventricular wall thickness. Cardiac diastolic function: E/A ratio

Seattle Angina Questionnaire score

8.3.3 Safety Endpoint

Assessment of safety endpoints will include:

All deaths.

All AEs occurred during treatment period.

Vital signs (heart rate, and blood pressure).

Clinical laboratory assessments from hematology and biochemistry samples.

Drug exposure.

8.4 Analysis Sets

Screen Population

The screening population will include all subjects who provide written informed consent and who undergo screening assessments, regardless of treatment status in the trial.

Intention-to-treat(ITT)

The ITT population is the subset of screen population, and it should include all subjects who receive at least one dose of trial treatment.

Per Protocol (PP)

The PP population will be the subset of the ITT population that is compliant with the protocol and characterized by criteria such as:

- 1) Measurement of the primary endpoint both at baseline and after twelve week treatment.
- 2) Absence of any major protocol deviation.

Major protocol violation will be defined in the Statistical Analysis Plan (SAP).

The PP population will be identified before database lock and will be used to test the primary endpoint. It will be considered a secondary population.

Safety

The safety population will include all subjects who received at least one dose of trial treatment.

8.5 Description of Statistical Analyses

8.5.1 Further Endpoints of Interest

No further endpoints of interest.

8.5.2 General Considerations

Statistical analysis will be performed using CRF data obtained until all subjects have Completed (or discontinued) the trial. The ITT population will be used primarily to present baseline characteristics and analyze efficacy data. Selected efficacy analyses will be repeated for the PP population.

If confidence intervals are to be calculated, these will be two-sided with a confidence probability of 95%, unless otherwise specified.

Continuous variables will be summarized using descriptive statistics, i.e., number of subject (N), mean, median, standard deviation (S.D.), 25th and 75th percentile (Q1-Q3), minimum and maximum. Qualitative variables will be summarized by means of counts and percentages. Unless otherwise stated, the calculation of proportions will be based on the sample size of the population of interest. Counts of missing observation will be included in the denominator and presented as a separate category.

For all variables, the baseline value will be defined as the last measurement taken prior to the first administration of treatment drug.

The dropouts and missing data will not be imputed.

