5.5 Criteria for Subject Withdrawal

5.5.1 Withdrawal from the Trial

Subjects are free to discontinue the trial at any time without giving their reasons.

A subject must be withdrawn in the event of any of the following:

Withdrawal of the subject's consent.

Participation in any other interventional trial during the duration of this trial

Withdrawal of the Investigational Medicinal Product

If a subject has failed to attend scheduled trial assessments, the Investigator must determine and record the reasons and the circumstances as completely and accurately as possible.

In any case, the appropriate Case Report Form (CRF) section must be completed.

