6.5.2 Non-permitted Medicines

Glyburide, which may influence the efficacy of nicorandil;

PDE-5 inhibitors, such as sildenafil citrate, vardenafil hydrochloride hydrate and tadalafil. The coadministration of these medicines with nicorandil may enhance hypotensive effect;

Soluble guanylate cyclase stimulator(s), such as riociguat. The co-administration with nicorandil may enhance hypotensive effect.

Some evidences showed that ranolazine could effect coronary microvascular function. So it should not be used during the study period and one month before the screening period.

Some injections that might have efficacy on patients' microvascular function are also not permitted during the study, such as alprostadil injection.

Any other additional concomitant therapy that becomes necessary during the trial and any change to concomitant drugs must be recorded in the corresponding section of the CRF, noting the name, dose, duration and indication of each drug.

If the administration of a non-permitted concomitant drug becomes necessary during the trial, e.g., because of AEs, the subject should withdraw from the study, the data should only be used for safety

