8.5.3 Analysis of Primary Endpoint

Paired t test will be used to evaluate the primary endpoint. The null hypothesis is that there is no difference between MFR at baseline and MFR after twelve week treatment. The alternative hypothesis is that the MFR after twelve week treatment is higher.

Furthermore, the mean value, standard deviation and two-sided 95% confidence interval (CI) will be calculated for the difference between MFR at baseline and after twelve week treatment.

This analysis will be done both in ITT population and PP population.

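### The primary test labelled ITT can contain only patients with both PET scans, so it is a completers analysis; separately, the safety-only clause in 6.5.2 conflicts with the ITT definition

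*Protocol*

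**What the plan says.** **Who is analysed.** Protocol 8.4 says of the ITT population that "it should include all subjects who receive at least one dose of trial treatment". Section 8.5.2 gives its role: "The ITT population will be used primarily to present baseline characteristics and analyze efficacy data". The per-protocol set in 8.4 adds, as its first criterion, "Measurement of the primary endpoint both at baseline and after twelve week treatment". Section 8.5.3 specifies a paired t test of MFR and states: "This analysis will be done both in ITT population and PP population".

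**Missing values.** Section 8.5.2 rules without qualification that "The dropouts and missing data will not be imputed".

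**Who leaves.** Section 5.5.1 lists "Withdrawal of the Investigational Medicinal Product" among the events after which a subject must be withdrawn from the trial. Section 5.5.2 withdraws the drug for therapeutic failure, adverse events, pregnancy, non-permitted drugs and non-compliance, among other reasons. Section 6.5.3 adds PCI, CABG and other surgery needing hospitalization.

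**When MFR is measured.** Sections 7.1 and 7.2.4 and Appendix I place PET at screening and at Visit 4 (week 12). No early-exit scan is scheduled.

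**Non-permitted drugs.** For a patient who needs one, 6.5.2 says "the subject should withdraw from the study, the data should only be used for safety".

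**The concern.** A paired t test needs two values per patient. A dosed patient who stops the drug leaves the trial, has no scheduled week-12 PET and may not be imputed. That patient belongs to the ITT set on paper but contributes nothing to the ITT test. A reader would take a result labelled ITT to describe all treated patients, and would take agreement between the ITT and per-protocol results as some reassurance about dropout. Neither inference would be sound.

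This matters more than usual because 8.1 allows for 30% dropout and there is no control arm, so any selective loss passes straight into the mean change. Section 5.2 also says the pilot is meant to supply parameters for later studies.

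The clause in 6.5.2 is a separate contradiction: it removes some dosed patients from efficacy, while 8.4 and 8.5.2 include every dosed patient without exception.

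**Working it through.** **1. The plan's own figure.** Inputs from 8.1: mean change 0.55, SD 0.56, two-sided alpha 0.05, power 0.80. Exact paired-t power (noncentral t, n − 1 df, noncentrality (0.55/0.56)·√n) is 78.9% at n = 10 and 83.5% at n = 11. The stated 11 reproduces, and it is a number of patients with both scans. With 15 recruited and 30% dropout, 15 × 0.70 = 10.5 completers are expected, so 10 or 11 analysed and 4 or 5 missing.

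**2. The two analysis sets in the primary test.**

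| | ITT | Per protocol |
|---|---|---|
| Definition (8.4) | at least one dose | ITT, both PETs, no major deviation |
| Able to enter the paired test | both PETs | both PETs |
| Patients without week-12 MFR | absent | absent |

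On the listed criteria, the two tests differ only by patients who have both scans and a major deviation.

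**3. How far the missing patients could move the result.** Take the planning values as observed: 11 completers, mean 0.55, SD 0.56. The SE is 0.56/√11 = 0.169, t = 3.26, p = 0.0086. Suppose the 4 missing patients differ from completers by an assumed shift s. The all-dosed mean is 0.55 + (4/15)·s.

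- *Direct shift* (SE 0.169, 10 df, critical t 2.228): significance is lost when the mean falls to 2.228 × 0.169 = 0.376, so s = (0.376 − 0.55) × 15/4 ≈ −0.65. Those who left would average 0.55 − 0.65 = −0.10.
- *Normal multiple imputation, Rubin pooling, small-sample df*:

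| s | All-dosed mean | p, multiple imputation | p, direct shift |
|---|---|---|---|
| 0 | 0.550 | 0.014 | 0.009 |
| −0.275 | 0.477 | 0.028 | 0.018 |
| −0.55 | 0.403 | 0.063 | 0.038 |
| −0.825 | 0.330 | 0.138 | 0.079 |
| −1.10 | 0.257 | 0.272 | 0.159 |

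With multiple imputation, p reaches 0.05 at s ≈ −0.47, a mean change of about 0.08 in those who left. With 10 completers and 5 missing, the crossing points are about −0.30 (multiple imputation) and −0.45 (direct).

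**4. Illustrative false positives.** N = 15, 30% dropout and SD 0.56 are the protocol's. No drug effect, the correlation ρ between poor MFR change and dropout, and the informative share are assumed. The bias in the completers' mean is ρ × 0.56 × φ(z_p)/(1 − p), where p is the informative dropout fraction. For p = 0.30 this is ρ × 0.278; for p = 0.15, with the other 15 points random, it is ρ × 0.154. Rejection rates are simulated (upper tail, nominal 2.5%).

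| ρ | All informative: bias; rejection | Half informative: bias; rejection |
|---|---|---|
| 0 | 0; 2.5% | 0; 2.5% |
| 0.3 | 0.08; 6.5% | 0.05; 4.3% |
| 0.5 | 0.14; 11.6% | 0.08; 6.0% |
| 0.7 | 0.19; 20.5% | 0.11; 8.3% |

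**5. The 6.5.2 contradiction.** No arithmetic applies. Section 6.5.2 confines these patients' data to safety; 8.4 and 8.5.2 place them in the main efficacy set. Both cannot hold. Because they are also withdrawn, they normally have no week-12 MFR, so the primary test changes only if one is scanned anyway, for instance when the drug use comes to light late. Baseline tables are affected too.

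**The case against.** The completers basis is not hidden. Section 8.1 sizes the trial on 11 patients, allows for dropout and lets the study close once 11 have completed; 8.5.2 says outright that nothing is imputed. An observed-data analysis is a defensible choice for a small single-arm pilot, and the protocol never claims that running ITT and per-protocol together deals with dropout. Reporting N for each summary (8.5.2) will show how many were analysed, and 5.5.1 already has reasons for missed assessments recorded. All of this stands, and it limits the point to a label and a blanket rule. It does not remove it: the protocol itself fixes the label and the unqualified bar, so an analysis plan that added an imputation-based sensitivity analysis would contradict 8.5.2.

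The size of any bias is assumed. No MFR is measured between screening and week 12, so no exit is triggered by an observed MFR change, and reasons such as pregnancy or unrelated surgery have no stated link to it. The 20.5% figure needs every dropout to be informative at ρ = 0.7. The crossing point also depends on the method: multiple imputation raises p from 0.009 to 0.014 before any shift is applied. The illustrations use 15 patients, whereas 5.1.1 and 6.3 speak of 20.

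The 6.5.2 clause has an understandable motive, since that section says of one excluded drug: "Some evidences showed that ranolazine could effect coronary microvascular function". MFR measured after such a drug is hard to interpret without a control arm. That explains the clause but does not reconcile it with 8.4.

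**Conclusion.** The point holds and should be fixed. As written, the primary test labelled ITT is a completers test, and neither of the two planned runs can show the effect of dropout. Section 6.5.2 contradicts 8.4 and 8.5.2, with little effect on the primary test.

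Three stronger readings are not supported.

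- A reader might infer that the sample size is wrong. It is not on this account, because the 11 in 8.1 already means completers.
- A reader might infer that the result will be biased upward. Therapeutic failure is one forced exit that could be linked to MFR, but the documents quantify no such link, and the bias is zero if dropout is unrelated to MFR change.
- A reader might infer that the protocol forbids a scan at exit. It does not; it merely schedules none, and a scan before week 12 would not be the primary endpoint.

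The sizes are therefore illustrative. At the planning values, the conclusion turns at a shift of about −0.47 to −0.65 with 4 of 15 missing, or −0.30 to −0.45 with 5 of 15. Upper-tail false positives at an assumed ρ of 0.3 to 0.7 run from about 6.5% to 20.5% if all dropout is informative, and from about 4% to 8% if half is.

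**What to change.** 1. In 8.5.2 and 8.5.3, call the paired test without imputation a completers (observed-data) analysis, and report how many dosed patients lack a week-12 MFR and for what reasons.
2. Confine the no-imputation rule to that analysis. Prespecify one sensitivity analysis of all dosed patients: impute missing changes from the completers' distribution shifted downward over a stated range, name the method, and report the shift at which the conclusion changes.
3. Reconcile 6.5.2 with 8.4 and 8.5.2, so that a single rule says which analysis sets hold patients who needed a non-permitted drug.

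The cost is wording in 6.5.2, 8.4, 8.5.2 and 8.5.3 plus one extra analysis. No additional patients, visits or scans are needed, and the rules on stopping treatment and on concomitant drugs are untouched. The drawback is that imputing about 4 values from 11 is imprecise, so this can serve only as a sensitivity analysis and not as a replacement for the primary test.
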